6.2 Methods of statistical analysis

6.2.1 Analysis sets

The Intent-to-Treat (ITT) set includes all participants who signed the ICF and meet inclusion/exclusion criteria.

6.2.2 Data analysis

Descriptive Statistics:

Patient baseline characteristics (e.g. age, sex, history of atrial fibrillation) were expressed as mean± standard deviation or median (quartiles) for continuous variables, and frequency and percentage for categorical variables.

Primary endpoint analysis:

Analyses of the primary endpoints will be performed based on mITT, with the 12-month complete closure rate of the WATCHMAN FLX device described by point estimates and their 95% confidence intervals, and a one-proportional hypothesis test ($\alpha = 0.05$) against a target value of $P_0 = 74.3\%$.

Secondary endpoint analysis:

Safety events (e.g. pericardial effusion, puncture site complications) were described by incidence rates and their 95% confidence intervals were calculated. Changes in quality of life were analyzed by chi-square test or paired t-test for time effects.

7. Ethical requirements and informed consent form

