19	BMI	Body Mass Index
20	LAAO	Left Atrial Appendage Occlusion

Summary of the Trial Protocol

Test Name	Evaluation of the Safety and Efficacy of Catheter Ablation After Left Atrial Appendage Occlusion with the WATCHMAN FLX Device
Sponsor	Department of Cardiology, Affiliated Hospital of Nantong University
Principal Investigator	[name]
Purpose of the test	
1. Main Purpose: To evaluate the safety and efficacy of catheter ablation performed one month after WATCHMAN FLX left atrial appendage occlusion (LAAO) in patients with non-valvular atrial fibrillation(AF).
 
2. Secondary Purpose: To investigate the impact of a two-surgery sequential treatment regimen on the recurrence rate of atrial fibrillation, the incidence of stroke, and the quality of life of patients, and to provide evidence-based support for decision-making in the clinical application of combined therapy.

Trial Population	Patients diagnosed with non-valvular AF who are scheduled to undergo sequential LAAO using the WATCHMAN FLX device and catheter-based ablation.
Trial Design	
This study is a prospective, single-arm, multicenter clinical trial designed to evaluate the safety and efficacy of catheter ablation performed one month after LAAO with the WATCHMAN FLX device. Approximately 210 patients with non-valvular AF who meet the indications for both transcatheter LAAO and catheter ablation will be enrolled across 10 research centers in China. The study procedures are outlined as follows: :
 
 Patient Screening and Enrollment: Eligible patients will undergo elective LAAO with the WATCHMAN FLX device (first procedure) after signing the informed consent form (ICF). Postoperative Management: Following the LAAO with the WATCHMAN FLX device, patients will undergo standard anticoagulation therapy for one month. If transesophageal echocardiography (TEE) reveals no device-related thrombosis (DRT) or residual flow >5 mm, the patient will undergo catheter ablation for atrial fibrillation (second procedure) one month after the initial LAAO.

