	
4. Quality of life improvement at 12 months measured by the Atrial Fibrillation Effect on Quality-of-Life (AFEQT) questionnaire: Improvement in quality-of-life score from baseline to 12 months following index ablation or AAD treatment, with a possible score range of 20 to 140 (higher scores indicate worse outcomes).

Entry Criteria	
 1) Age ≥ 18 years with a diagnosis of nonvalvular AF; 2) Eligible for indications for treatment with WATCHMAN FLX LAAO and transcatheter atrial fibrillation ablation; 3) Preoperative imaging evaluation showed that the LAA anatomy was suitable for WATCHMAN FLX device implantation; 4) Patients agreed to participate in the study and signed an ICF.
Exclusion criteria	
Patients meeting any of the following criteria were not eligible for this study:
 
 1) Presence of valvular heart disease or other structural heart disease that causes atrial fibrillation; 2) Preoperative detection of LAA thrombus or acute thrombotic event; 3) The patient has a severe bleeding tendency or a recent major bleeding event (e.g. gastrointestinal hemorrhage, cerebral hemorrhage, etc.); 4) Patients who are unable to complete postoperative follow-up (e.g. life expectancy less than 1 year or poor compliance); 5) Other serious diseases (e.g. liver and kidney failure, active infections, etc.) detected on preoperative examination; 6) Women who are pregnant or breastfeeding.
statistical analysis	
1. Sample size calculation:
 
The sample size was calculated based on the primary endpoint. The primary endpoint of this study was “12-month rate of complete closure of the block after WATCHMAN FLX LAAO (CT assessment).” Hypothesized target incidence $P_0 = 74.3\%$ and test incidence $P_1 = 84.3\%$. The significance level $\alpha = 0.05$ (one-sided) and test efficacy $1 - \beta = 80\%$ were calculated to be 200 cases able to fulfill the hypothesis test. Considering the 5% shedding rate, the total sample size was 210 cases.
 
2. Descriptive Statistics:
 
Patient baseline characteristics (e.g. age, sex, history of AF) were expressed as mean \pm standard deviation or median (quartiles) for continuous variables,

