6.1 Sample size calculation

The sample size was calculated based on the primary endpoint. The primary endpoint of this study was “12-month rate of complete closure of the block after WATCHMAN FLX LAAO (CT assessment)”.

Assuming that P_0 is the target incidence rate and P_1 is the trial incidence rate, P_0 was set to 74.3% (95% confidence interval: 65.9%~ 82.7%) based on the literature reports* and expert recommendations, the hypothesis testing was as follows:

$$H_0: P_1 \leq 0.743$$

$$H_1: P_1 > 0.743$$

A P_1 of 84.3% was set, significance level $\alpha = 0.05$ (one-sided), and test efficacy $1 - \beta = 80\%$. According to the sample size formula, 200 patients were needed in a single group to fulfill the statistical requirements. Considering a 5% loss-to-follow-up rate, the total sample size was set at 210 cases.

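### Quality-of-life change in the same patients may be tested by an ordinary chi-square or a paired t-test, with no rule for choosing; only the paired t-test fits the endpoint

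*Protocol*

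**What the plan says.** Section 6.2.2 (Data analysis, secondary endpoint analysis) states: "Changes in quality of life were analyzed by chi-square test or paired t-test for time effects". The Summary repeats the sentence under its secondary endpoint analysis.

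The endpoint is efficacy endpoint 4 in the Summary: "Improvement in quality-of-life score from baseline to 12 months following index ablation or AAD treatment". It is measured by the AFEQT, with a stated possible range of 20 to 140 and higher scores meaning worse quality of life. No responder cut-off or category is given.

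The design is a "prospective, single-arm, multicenter clinical trial", so there is no second group for a quality-of-life comparison. Section 3.1.2 names quality of life among the outcomes of the secondary purpose, with AF recurrence and stroke.

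**The concern.** The sentence lists two tests for one endpoint, and they answer different questions. The paired t-test works on each patient's own change. An ordinary chi-square compares two sets of counts as if they came from different people, and it needs categories that the protocol does not define.

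Baseline and 12-month scores from the same patient will normally be positively correlated. The variance that the chi-square assumes for the difference is then too large, its p-value is too large, and a real improvement can be missed. Cutting the score into categories loses further information. With no rule for choosing, the reported result could depend on which of the two tests is taken.

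**Working it through.** **Inputs from the protocol.** Section 6.1 says "200 patients were needed in a single group to fulfill the statistical requirements", and 210 are enrolled to allow for 5% loss. The check takes 200 complete baseline and 12-month pairs. The protocol gives no effect size, SD, within-patient correlation, significance level or power for quality of life, so there is no stated figure to reproduce.

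**Assumptions.** Two-sided 5% tests; bivariate normal scores with equal SD; score correlation ρ of 0.3, 0.5 and 0.7; for chi-square and McNemar, the score is split at the baseline median. The direction of improvement does not matter, because the tests are two-sided and the split is symmetric.

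**Step 1: true level of the chi-square.** With proportion p at both times, the chi-square uses variance 2p(1−p)/n for the difference. The true variance is 2p(1−p)(1−φ)/n, where φ is the correlation of the split scores. For a median split, φ = (2/π)·arcsin(ρ). The true level is 2·[1 − Φ(1.96/√(1−φ))].

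| Score correlation ρ | φ | True level, formula | True level, 20,000 simulations |
|---|---|---|---|
| 0.3 | 0.194 | 2.9% | 3.0% |
| 0.5 | 0.333 | 1.6% | 1.6% |
| 0.7 | 0.494 | 0.6% | 0.6% |

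McNemar's test and the paired t-test stay at about 5% throughout.

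**Step 2: power for a shift of 0.2 SD** (5,000 simulations per row).

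| ρ | Chi-square | McNemar | Paired t |
|---|---|---|---|
| 0.3 | 35% | 43% | 68% |
| 0.5 | 32% | 49% | 80% |
| 0.7 | 31% | 61% | 95% |

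At 0.3 SD and ρ = 0.5 the three figures are 69%, 83% and 99%.

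**Hand check at ρ = 0.5.**
- Chi-square: the shift moves the proportion from 0.500 to Φ(0.2) = 0.579, a difference of 0.079. The pooled proportion is 0.540, so the assumed SE is √(2·0.540·0.460/200) = 0.0498 and the critical difference is 1.96·0.0498 = 0.098. The true SE is about 0.0498·√(1−0.333) = 0.041. Power is about Φ((0.079−0.098)/0.041), or roughly 32–33%.
- Paired t: the SD of the change is √(2(1−0.5)) = 1, so the expected statistic is 0.2·√200 = 2.83. Power is about Φ(2.83−1.96) = 81%.

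Both agree with the simulation.

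**Step 3: where the loss comes from.** From chi-square to McNemar, which isolates the pairing, the gain is 43−35 = 8, 49−32 = 17 and 61−31 = 30 points. From McNemar to the paired t-test, which isolates the dichotomising, it is 68−43 = 25, 80−49 = 31 and 95−61 = 34 points.

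**The case against.** The best defence is that the sentence already names a valid test. The paired t-test is the only one of the two that fits a change in a numeric score, and none of the loss above arises if it is used. The wording may be shorthand for one test for categorical data and another for continuous data. The reference to time effects points to a repeated-measures question, and McNemar's statistic is itself a chi-square statistic. The exact form of a secondary test can also be left to a SAP, which is not shown here.

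Part of this stands. The protocol does not commit to the chi-square. The shorthand reading does not rescue that option, though: no categorical quality-of-life outcome is defined, nothing marks the chi-square as paired, and an ordinary chi-square would be wrong for categories measured twice in the same patients. This is a method that the protocol names, not a detail that it leaves out.

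Three stronger readings are tempting, and the documents support none of them.
- **That quality of life will be tested by chi-square.** It is one of two options.
- **That the chi-square would produce false claims of benefit.** Under positive correlation its own error runs the other way.
- **That the true levels are 1.9%, 0.6% and 0.03%.** These follow if 0.3, 0.5 and 0.7 are taken as correlations of the split variable. With a median split, that requires score correlations of sin(φπ/2) = 0.45, 0.71 and 0.89. The endpoint is a score, so the milder figures above are the relevant ones.

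**Conclusion.** The point holds in a limited form. The protocol lists an unsuitable test beside a suitable one for a within-patient change, with no rule for choosing and no categorical outcome to which the chi-square could apply. The harm is conditional on the chi-square being used. On the stated assumptions, its true level would then fall from 5% to between 3.0% and 0.6%, and its power for a 0.2 SD shift would be 33 to 64 points below that of the paired t-test (68−35 and 95−31). Pairing accounts for 8 to 30 of those points and dichotomising for the rest.

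The sizes depend on a correlation, a shift and a cut-off that the protocol does not give; the direction needs only positive within-patient correlation. The endpoint is secondary and drives neither the sample size nor the primary conclusion. It is a point to correct because the change is simple, not a threat to the trial's main result.

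**What to change.** In section 6.2.2 and in the matching Summary entry, remove the chi-square alternative. State that the 12-month minus baseline AFEQT score is analysed by a paired t-test, reported as mean change with a 95% CI. If a responder proportion at both times is also wanted, define the cut-off in advance and use McNemar's test with a CI for the paired difference.

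The cost is one sentence in two places, with no change to sample size. Any test of change needs AFEQT scores at both times. The visit table in section 4.1, as read here, shows no AFEQT row, so confirm that both assessments are scheduled. That is a separate matter and not a cost of this correction.

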7.1 Ethics Committee

Prior to the clinical study, the investigator is required to submit the clinical study protocol, informed consent and other relevant documents to the ethics committee of the hospital where the unit responsible for the clinical study is located. The clinical study can only be started after obtaining the approval of the ethics committee (sub-centers can also start the clinical study after accepting the ethics of the group leader center). Any modification of the study protocol must be approved by the Ethics Committee before implementation. Serious adverse events in the course of the clinical study should be submitted to the Ethics Committee in writing in a timely manner (each center will report according to the ethical requirements of each center, and back up to the group leader unit at the same time).

7.2 Informed consent form

Prior to enrollment in this study, the investigator must inform the subjects and their relatives about the details of the clinical study, including the content of the study, the purpose of the study, the expected efficacy, possible adverse events and countermeasures. Subjects will be enrolled only after they fully understand the study and sign an informed consent form. The informed consent form will be signed in duplicate by the study physician and the subject himself/herself or his/her legal representative, and each party will keep a copy.

8. Definition of adverse events and response measures

8.1 Adverse events

8.1.1 Definition of adverse events

An adverse event is an adverse medical condition or a worsening of a pre-existing medical condition that occurs after the implantation of an investigational device or during the course of treatment, whether or not there is a causal relationship between the condition and the investigational device. This adverse medical condition can be a symptom (e.g., nausea, chest pain), sign (e.g., tachycardia, hepatomegaly), or an abnormal test result (e.g., laboratory result, electrocardiogram). In a clinical study, an AE can encompass an adverse medical condition that occurs at any time, including the introductory or washout period, even when no study treatment is given.

8.1.2 Determination of severity of adverse events

Mild: Does not interfere with daily activities;

Moderate: interferes with daily activities;

Severe: Loss of ability to perform daily activities.

8.1.3 Response to adverse events

All adverse events occurring during the study period must be faithfully recorded in the Adverse Event Form, and the investigator should give targeted treatment for the adverse event and follow up until the symptoms have disappeared or stabilized.

8.2 Serious Adverse Events

8.2.1 Definition of serious adverse events

A serious adverse event is defined as an AE that occurs within any study phase (i.e. introductory, treatment, washout, follow-up) that meets 1 or more of the following criteria.

- Lead to death
- Immediately life-threatening
- Subject hospitalization or extension of existing hospitalization is required
- Cause permanent or significant disability or dysfunction
- Cause congenital malformations or birth defects
- Significant medical events that may jeopardize the health of the subject or require medical intervention to avoid the above outcomes

8.2.2 Reporting process

In the event of a serious adverse event in a clinical trial, the investigator shall immediately take appropriate therapeutic measures for the subject, and at the same time report in writing to the drug clinical trial management department of the clinical trial organization to which it belongs, and by which the sponsor shall be notified in writing. The clinical trial management department shall, within 24 hours, report in writing to the appropriate ethics committee as well as the food and drug supervision and management

Evaluation of the Safety and Efficacy of Catheter Ablation Following Left Atrial Appendage Occlusion Using the WATCHMAN FLX Device
department of the province, autonomous region and municipality directly under the central government where the clinical trial organization is located and the competent department of health and family planning. In the case of a death, the clinical trial organization and the investigator shall provide the ethics committee and the sponsor with all the information required.

8.3 Unintended Adverse Reactions

Unintended adverse reactions are defined as serious adverse reactions affecting health, safety, or any life-threatening, death-causing problems or deaths arising from or associated with the investigational device, which were not identified in the prior study plan or application with respect to their severity or occurrence; or any other unintended serious device-related problems associated with patient rights, safety.

During the study, the investigator must, as far as possible, refer any occurrence of unintended adverse reactions to the Principal Investigator and the Ethics Committee. Serious adverse reactions were reported within 24 hours. The Principal Investigator and Ethics Committee inform the investigator of any unintended device adverse reactions that occur.

8.4 Expected adverse reactions

The following anticipated complications may result from the occluder or antithrombotic medications:

1, Device related thrombosis 2, Ischemic stroke 3, Pericardial effusion 4, Hemorrhagic stroke 5, Cardiac tamponade 6, Nuisance bleeding 7, Hemorrhage 8, Death

8.5 Duration of follow-up after adverse events

All adverse events are to be followed until resolved or until a stable clinical endpoint is achieved

8.6 Security incident audits

To ensure the safety of subjects during the conduct of the study, the safety of the clinical trial will be assessed by analyzing and reviewing major safety events at regular intervals during the conduct of the study. Given that all-cause mortality, ischemic stroke, and major bleeding events are the most relevant adverse events related to device or procedure safety, the focus will be on monitoring and evaluating these three types of events. Once the number of subjects with safety events reaches or exceeds the expected number of cases, safety investigations and appropriate treatment measures will be triggered.

References:

Annex I: CHA₂DS₂-VASc Score for Nonvalvular Atrial Fibrillation

Stroke Risk

risk factor	Scoring (points)
Congestive heart failure/left ventricular dysfunction (C)	1
Hypertension (H)	1
Hypertension (H)	2
Diabetes (D)	1
Stroke/TIA/thromboembolism history (S)	2
Vascular disease history (V)	1
Age 65-74 (A)	1
Sex (Female, Sc)	1
maximum	9

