3.2 Selection of subjects

3.2.1 Entry Criteria

- 1) Age ≥ 18 years with a diagnosis of nonvalvular AF;
- 2) Eligible for indications for treatment with WATCHMAN FLX LAAO and transcatheter atrial fibrillation ablation;
- 3) Preoperative imaging evaluation showed that the LAA anatomy was suitable for WATCHMAN FLX device implantation;
- 4) Patients agreed to participate in the study and signed an ICF.

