Annex II: HAS-BLED Score

Clinical features	Scoring (points)
Hypertension (H)	1
Abnormal liver and kidney function (1 point each, A)	1 or 2
Stroke(S)	1
Bleeding (B)	1
INR values are volatile (L)	1
Elderly (e.g. age >65 years, E)	1
Drugs or alcoholism (1 point each, D)	1
maximum	9

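### The Annex I and Annex II scoring tables contradict their own totals: Annex I lists hypertension twice and gives no points from age 75, and Annex II's drugs/alcohol row disagrees with its own label (minor)

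*Protocol*

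**What the plan says.** The visit table in Protocol section 4.1 marks both CHA₂DS₂-VASc and HAS-BLED with a filled triangle at Visit 1, the symbol for items that are actively collected. Annexes I and II are the only scoring rules that the protocol gives for them.

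Annex I includes "Congestive heart failure/left ventricular dysfunction (C) 1", "Hypertension (H) 1", "Hypertension (H) 2", "Stroke/TIA/thromboembolism history (S) 2", "Vascular disease history (V) 1" and "Sex (Female, Sc) 1". Diabetes has 1 point, and the single age row gives 1 point for 65 to 74. The stated maximum is 9.

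Annex II gives the liver/kidney row 1 or 2 points, one for each organ. The drugs/alcohol row is labelled in the same way but reads "Drugs or alcoholism (1 point each, D) 1". The stated maximum is again 9.

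The entry criterion nearest to these scores is "Eligible for indications for treatment with WATCHMAN FLX LAAO and transcatheter atrial fibrillation ablation" (section 3.2.1). It names neither score and sets no cut-off.

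**The concern.** A site that follows Annex I literally meets two values for one condition and finds no value at all for an age group that an atrial fibrillation trial can expect to enrol. A man of 74 with no other factor scores 1; at 75 he scores 0. A site that scores from general knowledge would not make this mistake. Two of the 10 centres could therefore record different values for the same patient, and a summary of total scores would not reveal it.

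At stake is the description of the enrolled population. The trial has one arm and reports stroke, systemic embolism and major bleeding over 12 months. With no control group, readers will look to baseline stroke and bleeding risk to interpret those rates.

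**Working it through.** **Annex I, inputs (printed points).** Heart failure 1, hypertension 1, hypertension again 2, diabetes 1, stroke history 2, vascular disease 1, age 65–74 1, female sex 1. Stated maximum 9.

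| Reading | Sum | Total |
|---|---|---|
| All rows added | 1+1+2+1+2+1+1+1 | 10 |
| Hypertension once, at 1 | 1+1+1+2+1+1+1 | 8 |
| Hypertension once, at 2 | 1+2+1+2+1+1+1 | 9 |
| 2-point row is age ≥75, exclusive of 65–74 | 1+1+2+1+2+1+1 | 9 |

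The stated 9 is not reproduced by adding the rows. Two readings do reproduce it, so the total alone does not decide between them.

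The annex title does. In CHA₂DS₂-VASc the letters run C, H, A₂, D, S₂, V, A, Sc. The table rows run heart failure, hypertension, hypertension, diabetes, stroke, vascular disease, age 65–74, sex. Matched in order:

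- A₂ falls on the second hypertension row, which carries 2 points.
- S₂ falls on the stroke row, which also carries 2 points.
- The later A falls on the 65–74 row.

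The name calls for two A rows and the table has one. The age band that the 65–74 row leaves open above it starts at 75. The reading with hypertension once at 2 fits the total but leaves A₂ without a row and age 75 or over without points.

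**Size of the error in Annex I, against the age ≥75 reading.**

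- Age 75 or over: 0 printed against 2, a difference of −2 under any reading of the printed labels.
- Hypertension: 1, 2 or 3 printed (first row, second row, both added) against 1, a difference of 0, +1 or +2.
- Both together: −2, −1 or 0.
- Example, hypertensive man of 70: 1 for age plus 1, 2 or 3 gives 2, 3 or 4, against 1+1 = 2.
- Example, woman of 78 with no other factor: 1, against 1+2 = 3.

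**Annex II, inputs (printed points).** Hypertension 1, liver/kidney up to 2, stroke 1, bleeding 1, labile INR 1, elderly 1, drugs/alcohol 1. Stated maximum 9.

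- Points column: 1+2+1+1+1+1+1 = 8.
- Following the row's label, with drugs/alcohol up to 2: 1+2+1+1+1+1+2 = 9.

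The label agrees with the stated maximum and the points cell does not. A patient with both factors gets 2 by the label and 1 by the cell.

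**The case against.** The strongest case on the other side is that these are slips of the pen with no effect on the trial's conclusions. Much of that stands.

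- **Eligibility.** A reader might infer that the wrong patients are enrolled because the tables misstate who has an indication for LAAO. The protocol does not support that. Neither the entry nor the exclusion criteria name a score, a cut-off or an annex. An effect on entry would arise only if sites judged the LAAO indication from these tables, and the protocol does not say that they do.
- **Endpoints and analysis.** No endpoint or planned analysis in the protocol uses either score. Section 8.6 compares safety events with an expected number, but does not say that the number comes from these scores.
- **Other risk information.** A reader might take the two scores as the only record of baseline risk. They are not: section 4.1 also collects demographics, relevant medical history, renal function, INR and medication at screening.
- **Worst-case readings.** It is tempting to say that every hypertensive patient gains 2 points. That requires adding both rows. It is also tempting to say that Annex II cannot reach 9. Only its points column cannot; the row label can.
- **Familiarity.** Cardiology sites may recognise the slip and score correctly. This is plausible, but the protocol does not ensure it.
- **Reading from PDF.** The tables were read by a program, so the repeated row might be an artefact. It must be checked against the original. The Annex II mismatch lies in a separate table and does not depend on that check.

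What does not fall away is that the protocol requires two scores and supplies scoring tables that disagree with themselves.

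**Conclusion.** The contradiction is real and minor. Followed as printed, Annex I gives patients aged 75 or over 2 points too few and hypertensive patients 0 to 2 too many. Annex II may cost a patient with both a drug and an alcohol factor 1 point. The direct consequence is misrecorded baseline stroke and bleeding risk, which matters somewhat in a trial without controls. The sample size, the primary endpoint and its test are untouched.

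This rests on three assumptions: the printed tables match the original document, sites score from the annexes, and the 2-point row is the A₂ item in the score's name. The last is well supported by row order and by the total of 9. Whether any site has mis-scored a patient cannot be known from the protocol.

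**What to change.** 1. Check both annex tables against the original document.
2. In Annex I, relabel the 2-point hypertension row as age 75 or over, exclusive of the 65–74 row, so that the maximum is 9.
3. In Annex II, change the points cell of the drugs/alcohol row to 1 or 2, so that it agrees with its label and the maximum is 9.
4. Re-check scores already recorded with the printed tables.

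The cost is two cells and a check of existing records. For CHA₂DS₂-VASc the check can draw on the demographics and history collected at screening. Deriving the scores centrally from components is optional. For HAS-BLED it might need added data items, because the history list in section 4.1 does not name prior bleeding, alcohol use or INR lability.
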